**Signature**  
\_\_\_\_\_  
\_\_\_\_\_  
\_\_\_\_\_**Date**  
\_\_\_\_\_  
\_\_\_\_\_

For internal use only

-----Checksum-----!Ver.!Created On - -  
a52942bb02c0cbdc9274680e4d203654ee8eb36e 4.0 7/6/2018 7:02:05 AM - -  
-----

**CONFIDENTIAL**204913 (NTHI-MCAT-006 EXT:001)  
Protocol Amendment 1 Final**Protocol Amendment 1 Rationale**

Amendment number:	Amendment 1
Rationale/background for changes:	

 
• Table 3 of the protocol (Intervals between study visits) was updated as follow:           
 
- Optimal length of interval and allowed intervals were updated to avoid the risk of accumulating up to five shortest or longest allowed intervals with possible anticipation/delay of subject's last visit +/- 100 days from the optimal length of the study.
 
- Footnote 1 was added to Table 3 to specify that the indication of the month of the visit (i.e. Visit 1 [Month 20]) in the Interval column is an approximate period (label) and not an exact requirement to plan the visit during a specific study month.
 
- Footnote 2 was added to Table 3 to define how to count a calendar month for planning the visits.
 
 
 
• The definition of "calendar month" was added to the Glossary of terms.
 
• The protocol was aligned with the Statistical Analysis Plan Amendment, regarding the model used for the immunogenicity analysis.
 
• Table 5 and the laboratory assays appendix were updated with new cut-off values, since new optimized assays have been developed during the study. As the ANCOVA model used for the statistical analysis will include the group category as fixed effects and the pre-Dose 1 concentration in NTHi-Mcat-001 study as regressor, it is to be noted that pre-Dose 1 antibody concentrations in NTHi-Mcat-001 study were reported using the first generation ELISA with a cut-off of 7 EL.U/mL. However, the 2 assay versions have been shown to be technically aligned, allowing the exploratory comparison of anti-PilA ELISA data between NTHi-Mcat-001 and NTHi-Mcat-006 studies.
 
• The list of contributors was updated.
 
• Minor edits have been made in alignment with the GSK protocol template.
 
	

**CONFIDENTIAL**204913 (NTHI-MCAT-006 EXT:001)  
Protocol Amendment 1 Final**Protocol Amendment 1 Investigator Agreement**

I agree:

**4. Sponsor Study Contact for Reporting of a Serious Adverse Event**

GSK Biologicals Central Back-up Study Contact for Reporting SAEs: refer to protocol Section [8.3.2](#).

**CONFIDENTIAL**204913 (NTHI-MCAT-006 EXT:001)  
Protocol Amendment 1 Final**SYNOPSIS**

Detailed Title	A phase 1, multicentre, long term follow-up study up to 4 years after study vaccination to assess immunogenicity and safety of the investigational GSK Biologicals' GSK3277511A vaccine in adults.
Indication	Active immunisation for the reduction of frequency of moderate and severe acute exacerbations of COPD in patients with previous history of COPD.
Rationale for the study and study design	
 
Rationale for the study: The purpose of this long-term follow-up of a Phase I study is to evaluate the kinetics of the antibody response to NTHi-Mcat antigens and long-term safety, in subjects aged between 50–71 years at the time of enrolment in the NTHi-Mcat-001 study, and who were having a significant smoking history (<math>\geq 10</math> pack-years). These subjects were previously exposed to two adjuvanted formulations of the NTHi-Mcat vaccine administered according to a 0, 2 months schedule in the NTHi-Mcat-001 (201281) study. The subjects that had received saline placebo controls will also be included in this follow-up study to make comparisons with the investigational vaccines. No vaccinations will be administered in this trial.
 
Rationale for the study design: Only the subjects included in STEP 2 of the primary vaccination study (NTHi-Mcat-001/ 201281) will be enrolled in this follow-up study. These study groups were chosen because the subjects included reflect the primary age range (50-71 years old at the time of enrolment in the NTHi-Mcat-001 study) of the target population (COPD patients with a previous history of exacerbation). STEP 2 of the NTHi-Mcat-001 study included 90 healthy adults, 50–71 years old at the time of enrolment, with a smoking history of at least 10 pack-years, either receiving placebo control, or one of two AS01E adjuvanted formulations, i.e. 10 <math>\mu</math>g of PD, 10 <math>\mu</math>g of PE-PilA and 10 <math>\mu</math>g of UspA2 (Group 10-10-10-AS) or 10 <math>\mu</math>g of PD, 10 <math>\mu</math>g of PE-PilA and 3.3 <math>\mu</math>g of UspA2 (Group 10-10-3-AS) (30/group).
 

Objective(s)	
Primary
 
 
To assess the persistence of humoral antibodies up to 3 years after the last planned visit (Month 14) in the NTHi-Mcat-001 study.
 

**CONFIDENTIAL**204913 (NTHI-MCAT-006 EXT:001)  
Protocol Amendment 1 Final**Secondary**

- To assess the safety of the investigational NTHi-Mcat vaccine in terms of serious adverse events and potential immune-mediated diseases up to 3 years after the last planned visit (Month 14) in the NTHi-Mcat-001 study.
- Study design
  - Experimental design: Phase I, controlled, multi-centric, single-country, long term follow-up study with three parallel groups from the NTHi-Mcat-001 study.
  - Duration of the study: For each subject, the study will last approximately 30 months.
  - Epoch 001: Long-term follow-up starting at Visit 1 (Month 20) and ending at Visit 6 (Month 50).
  - Primary completion Date (PCD): Visit 6 (Month 50).
  - End of Study (EoS): Last testing results released of samples collected at Visit 6, will be achieved no later than 8 months after last subject last visit (LSLV).
  - Study groups of the NTHi-Mcat-001 study:
    - 10-10-10-AS: Up to 30 subjects who have received two doses of the AS01E-adjuvanted GSK Biologicals' NTHi-Mcat investigational vaccine during STEP 2 of NTHi-Mcat-001 study containing 10 $\mu$ g of PD, PE-PilA and UspA2.
    - 10-10-3-AS: Up to 30 subjects who have received two doses of the AS01E-adjuvanted GSK Biologicals' NTHi-Mcat investigational vaccine during STEP 2 of NTHi-Mcat-001 study containing 10 $\mu$ g of PD, 10 $\mu$ g of PE-PilA, and 3.3 $\mu$ g of UspA2.
    - PLACE2: Up to 30 subjects who have received two doses of placebo (saline solution) during STEP 2 of the NTHi-Mcat-001 study.

**Synopsis Table 1    Study groups and epochs foreseen in the study**

Study Groups*	Number of subjects	Epoch
		Epoch 001
10-10-10-AS	up to 30	x
10-10-3-AS	up to 30	x
PLACE2	up to 30	x

\*Study groups of NTHi-Mcat-001 study. No vaccinations will be administered in this trial.

**CONFIDENTIAL**204913 (NTHI-MCAT-006 EXT:001)  
Protocol Amendment 1 Final

- Control: placebo control

Blinding: open. This is a long-term follow-up study following up on the observer blinded NTHi-Mcat-001. Data from the NTHi-Mcat-001 study may still be blinded at the start of this study; therefore, at the time of enrolment, subjects may not be aware of the study group to which they were assigned in the NTHi-Mcat-001 study.

- Sampling schedule: Blood samples for humoral immunogenicity will be collected from all subjects at Visit 1 (Month 20), Visit 2 (Month 26), Visit 3 (Month 32), Visit 4 (Month 38), Visit 5 (Month 44) and Visit 6 (Month 50).
- Type of study: extension of other protocol(s) (NTHi-Mcat-001 [201281]).
- Data collection: Electronic Case Report Form (eCRF)
- Safety monitoring: Follow-up of Serious Adverse Events (SAEs) and potential immune-mediated diseases (pIMDs). Refer to Section 8.4 for detailed description of safety monitoring.

**Number of subjects** Up to 90 subjects who were exposed in STEP 2 of study NTHi-Mcat-001 (204913) and who agree to participate in the present study will be enrolled at the same study centres in Belgium.

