**Blinding:**

A procedure in which one or more parties to the trial are kept unaware of the treatment assignment in order to reduce the risk of biased study outcomes. The level of blinding is maintained throughout the conduct of the trial, and only when the data are cleaned to an acceptable level of quality will appropriate personnel be unblinded or when required in case of a serious adverse event. In an open-label study, no blind is used. Both the investigator and the subject know the identity of the treatment assigned. In a single-blind study, the investigator and/or his staff are aware of the treatment assignment but the subject is not. In an observer-blind study, the subject and the site and sponsor personnel involved in the clinical evaluation of the subjects are blinded while other study personnel may be aware of the treatment assignment (see Section 5.3 for details on observer-blinded studies). In a double blind study, the subject, the investigator and sponsor staff who are involved in the treatment or clinical evaluation of the subjects and the review or analysis of data are all unaware of the treatment assignment.

Partially-blind is to be used for study designs with different blinding levels between different groups, e.g. double-blinded consistency lots which are open with respect to the control group.

**CONFIDENTIAL**204913 (NTHI-MCAT-006 EXT:001)  
Protocol Amendment 1 Final

Calendar month (Amended 28 June 2018)	A period from a specified day in one month to the day numerically corresponding to that day in the following month independently on the specific length of the month (i.e. from the 5th of February to the 5th of March)
Current smoker:	A person who is currently smoking or who has stopped smoking within the past 6 months.
Eligible:	Qualified for enrolment into the study based upon strict adherence to inclusion/exclusion criteria.
End of Study (Synonym of End of Trial):	For studies without collection of human biologicals samples or imaging data EoS is the Last Subject Last Visit (LSLV).  For studies with collection of Human Biologicals Samples or imaging data, EoS is defined as the date of the last testing/reading released of the Human Biological Samples or imaging data, related to primary and secondary endpoints. EoS must be achieved no later than 8 months after LSLV

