**Table 1 Study groups and epochs foreseen in the study**

Study groups*	Number of subjects	Epoch
		Epoch 001
10-10-10-AS	up to 30	x
10-10-3-AS	up to 30	x
PLACE2	up to 30	x

\*Study groups of NTHi-Mcat-001 study. No vaccinations will be administered in this trial.

- **Control:** placebo control.
- **Blinding:** This is a long-term follow-up study following up on the observer blinded NTHi-Mcat-001. Data from the NTHi-Mcat-001 study may still be blinded at the start of this study; therefore, at the time of enrolment, subjects may not be aware of the study group to which they were assigned in the NTHi-Mcat-001 study.
- **Sampling schedule:** Blood samples for humoral immunogenicity will be collected from all subjects at Visit 1 (Month 20), Visit 2 (Month 26), Visit 3 (Month 32), Visit 4 (Month 38), Visit 5 (Month 44) and Visit 6 (Month 50).
- **Type of study:** extension of other protocol(s) (NTHi-Mcat-001 [201281]).
- **Data collection:** Electronic Case Report Form (eCRF)
- **Safety monitoring:** Follow-up of Serious Adverse Events (SAEs) and potential immune-mediated diseases (pIMDs). Refer to Section 8.4 for detailed description of safety monitoring.

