## **5.3. Method of blinding**

No vaccine exposure and randomization is overseen in this study, and thus no blinding procedure is in place. However, the laboratory in charge of the immunogenicity testing will be blinded to the treatment subjects received in parent trial, and codes will be used to link the subject and study (without any link to the treatment attributed to the subject) to each sample.

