**8.1.4. Adverse events of specific interest****8.1.4.1. Potential immune-mediated diseases**

Potential immune-mediated diseases (pIMDs) are a subset of AEs that include autoimmune diseases and other inflammatory and/or neurologic disorders of interest which may or may not have an autoimmune aetiology. AEs that need to be recorded and reported as pIMDs include those listed in [Table 7](#).

However, the investigator will exercise his/her medical and scientific judgement in deciding whether other diseases have an autoimmune origin (i.e. pathophysiology involving systemic or organ-specific pathogenic autoantibodies) and should also be recorded as a pIMD.

**CONFIDENTIAL**204913 (NTHI-MCAT-006 EXT:001)  
Protocol Amendment 1 Final**Table 7 List of potential immune-mediated diseases**

Neuroinflammatory disorders	Musculoskeletal disorders	Skin disorders

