## **8.2. Detecting and recording serious adverse events**

### **8.2.1. Time period for detecting and recording serious adverse events**

The time period for collecting and recording SAEs will begin at the first study visit and will end at study conclusion following last study visit for each subject. See Section [8.3](#) for instructions on reporting of SAEs.

All SAEs leading to withdrawal from the study will be collected and recorded from the time of the first study visit.

All SAEs related to the study vaccine(s) that occurred since the end of the primary study NTHi-Mcat-001 (201281) will be collected retrospectively, after informed consent is obtained.

In addition to the above-mentioned reporting requirements and in order to fulfil international reporting obligations, SAEs that are related to study participation (i.e. protocol-mandated procedures, invasive tests, a change from existing therapy) or are related to a concurrent GSK medication/vaccine will be collected and recorded from the time the subject consents to participate in the study until she/he is discharged from the study.

The time period for collecting and recording of pIMDs will begin at the first study visit and will end at study conclusion following the last study visit. See section [8.3.4](#) for instructions on reporting of pIMDs.

An overview of the protocol-required reporting periods for SAEs is given in [Table 8](#).

**CONFIDENTIAL**204913 (NTHI-MCAT-006 EXT:001)  
Protocol Amendment 1 Final**Table 8 Reporting periods for collecting safety information**

Event	Visit 1	Visit 2	Visit 3	Visit 4	Visit 5	Visit 6	Study Conclusion
	Month 20	Month 26	Month 32	Month 38	Month 44	Month 50	Month 50
SAEs							
pIMDs							
Intercurrent medical conditions*							

\* Medical conditions that, by potentially altering the immune response of a subject (except pregnancies), may lead to a subject being eliminated from analysis.

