**8.2.3.2.2. Assessment of causality**

The investigator is obligated to assess the relationship between study vaccine(s) and the occurrence of each SAE using clinical judgement. In case of concomitant administration of multiple vaccines/products, if possible, the investigator should specify if the SAE could be causally related to a specific vaccine/product administered (i.e investigational, control/placebo or co-administered vaccine). When causal relationship to a specific vaccine(s)/product(s) cannot be determined the investigator should indicate the SAE to be related to all products.

Alternative plausible causes, such as natural history of the underlying diseases, concomitant therapy, other risk factors, and the temporal relationship of the event to the study vaccine(s) will be considered and investigated. The investigator will also consult the IB and/or SmPC for marketed products to determine his/her assessment.

There may be situations when a SAE has occurred and the investigator has minimal information to include in the initial report to GSK Biologicals. However, it is very important that the investigator always makes an assessment of causality for every event prior to submission of the Expedited Adverse Events Report to GSK Biologicals. The investigator may change his/her opinion of causality in light of follow-up information and update the SAE information accordingly. The causality assessment is one of the criteria used when determining regulatory reporting requirements.

If an event meets the criteria to be determined as 'serious' (see Section [8.1.2](#)), additional examinations/tests will be performed by the investigator in order to determine ALL possible contributing factors for each SAE.

**CONFIDENTIAL**204913 (NTHI-MCAT-006 EXT:001)  
Protocol Amendment 1 Final

Possible contributing factors include:

- Medical history.
- Other medication.
- Protocol required procedure.
- Other procedure not required by the protocol.
- Erroneous administration.
- Other cause (specify).

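### The sites have no rule for keeping the parent-study blind while they judge pIMDs and vaccine-relatedness, and events before Visit 1 are selected on relatedness under two different terms

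*Protocol*

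**What the plan says.** The synopsis states "Blinding: open. This is a long-term follow-up study following up on the observer blinded NTHi-Mcat-001". The protocol glossary says what an open study means: "In an open-label study, no blind is used. Both the investigator and the subject know the identity of the treatment assigned". Protocol 5.3 gives the reason, "No vaccine exposure and randomization is overseen in this study, and thus no blinding procedure is in place", and makes one exception: "the laboratory in charge of the immunogenicity testing will be blinded to the treatment subjects received in parent trial".

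The blinding bullet in protocol section 3 does not use the word open. It says "Data from the NTHi-Mcat-001 study may still be blinded at the start of this study", so that subjects may not know their group when they enrol. Neither document says when, or under what rule, the parent allocation is released to sites or subjects.

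On safety, protocol 8.2.1 collects SAEs and pIMDs from Visit 1. Before Visit 1 it is selective: "All SAEs related to the study vaccine(s) that occurred since the end of the primary study NTHi-Mcat-001 (201281) will be collected retrospectively", once consent has been given. There is no look-back for pIMDs. SAP 8.2 nevertheless starts the safety data at Month 14 in every analysis. SAP 6.3.1 adds SAEs or pIMDs related to the *investigational vaccine* of the parent study if they are reported after the parent study's last visit and after consent to this one.

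**The concern.** The parent allocation defines the groups in every by-group table. That no vaccine is given in this study is therefore not a reason to release it. Nothing at the sites requires it either. Protocol Table 2 sets the same visits, samples and safety recording for everyone, SAP 8.2 keeps interim results internal, and protocol 10.9.1 gives investigators the integrated report only after the final analysis.

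Without a rule, site staff and subjects may learn the assignment part-way through, at different times in different centres. The direction of any effect is foreseeable: protocol 1.2.1 says pIMDs are watched closely because an adjuvant was used. A known adjuvant recipient may be examined and worked up more readily than a known saline recipient. A by-group difference in pIMDs could then partly reflect how hard people looked.

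A separate problem is that events from Month 14 to Month 20 enter only if someone judges them related, and the protocol and SAP name different products as the reference for that judgement.

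**Working it through.** **Step 1. What the site decides.**
- Unlisted pIMDs: "the investigator will exercise his/her medical and scientific judgement in deciding whether other diseases have an autoimmune origin" (protocol 8.1.4.1).
- Listed pIMDs: a suspected case does not count until the diagnosis is definitive and alternatives are excluded or less likely (8.1.4.1), so the amount of work-up matters.
- Examination after Visit 1 happens only on a subject's complaint or the investigator's decision (5.6.5).
- Detection begins with an open question about feeling different (8.2.3.1).
- Seriousness of important medical events is a matter of judgement (8.1.2).
- Relatedness: "The investigator is obligated to assess the relationship between study vaccine(s) and the occurrence of each SAE using clinical judgement" (8.2.3.2.2).

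No blinded adjudication is described. SAP 11.2.4 has a sponsor role review AEs by reference to treatment group, which is not a blinded backstop.

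**Step 2. What is protected.** The primary antibody endpoint is read by a blinded laboratory. The SAE endpoint (protocol 10.2) is any SAE, whatever its cause. Most pIMDs come from the fixed list in Table 7.

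**Step 3. Look-back, worst case.** Protocol 10.3 gives no sample size or event rate, so there is no figure to reproduce. Inputs from the documents: an objective window of Month 14 to 50 (36 months), Visit 1 at Month 20, and up to 60 vaccinated and 30 placebo subjects. Assumed: a 36-month risk *r*, equal in all groups and constant over time; every vaccine-group look-back event counted and no placebo one.

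- Look-back share: 6/36 = 16.7%.
- Apparent risk ratio: *r* / (*r* × 30/36) = 1.20, whatever *r* is.
- If only a fraction *f* of vaccine-group look-back events is judged related, the ratio is (30 + 6*f*)/30. With *f* = 0.5 this is 33/30 = 1.10.
- Placebo events lost: 30 × *r*/6. Chance of at least one to lose: 1 − (1 − *r*/6)^30.

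| Assumed *r* | Expected counted, 60 vaccinated | Expected counted, 30 placebo | Placebo events lost | Chance of at least one to lose |
|---|---|---|---|---|
| 2% | 1.2 | 0.5 | 0.1 | 9.5% |
| 5% | 3.0 | 1.25 | 0.25 | 22.2% |
| 10% | 6.0 | 2.5 | 0.5 | 39.6% |
| 20% | 12.0 | 5.0 | 1.0 | 63.8% |

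**Step 4. Unequal detection after Visit 1.** If known placebo subjects have relative detection *a*, the apparent ratio is 1/*a* and the expected loss is 30 × risk × (1 − *a*). For *a* = 0.9, 0.75 and 0.5 the ratio is 1.11, 1.33 and 2.0. The loss is 0.15, 0.375 and 0.75 events at an assumed 5% risk, and 0.30, 0.75 and 1.5 at 10%. The ratio only restates the assumed *a*. The documents give no basis for choosing it.

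**Step 5. Sampling error for comparison.** With zero events the upper limit of the exact 95% interval is 1 − 0.025^(1/*n*): 11.6% for *n* = 30 and 6.0% for *n* = 60. With 0 of 30 in placebo, 8 of 60 vaccinated subjects would need an event for Fisher's exact test to fall below 0.05 (p = 0.048). One placebo event is 1/30 = 3.3 percentage points.

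**The case against.** The strongest reply is that little in this study can be biased. The only vaccine–placebo comparison specified is the GMC ratio for stopping, measured blind. Safety is tabulated with exact intervals and no between-group test (SAP 6.3.1), and all analyses are descriptive (SAP 7). Hospitalisation in doubt is resolved towards serious (protocol 8.1.2). A standard questionnaire supports pIMD reporting. All of this stands and limits the size of the point. It does not supply the missing rule, and sampling error does not remove a bias that runs in one direction.

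Four stronger readings are tempting and are not supported:

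- *Investigators know the allocation throughout.* A reader might infer this from the glossary. But the synopsis and section 3 allow that the parent blind still holds at the start, and SAP 8.2 has an ANOVA fallback in case parent data are not available and cleaned at Interim 1. What is established is that they may come to know.
- *Placebo look-back events are excluded by design.* Look-back events are collected after consent, so around Visit 1, when relatedness may still be judged blind. The glossary's study vaccine/product includes placebo used as a reference, and protocol 8.2.3.2.2 names control/placebo as a possible cause. The exclusion follows only if the allocation is known; the SAP term then reinforces it.
- *The secondary endpoints as a whole rest on site judgement.* Step 2 shows otherwise.
- *Subjects who learn that they had placebo will decline or drop out.* Neither document gives data on this, and subjects may not know their group at enrolment.

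**Conclusion.** The point holds in a limited form. The study is declared open, sites have no blinding procedure, and no release time for the parent allocation is stated. The possible bias is confined to pIMD ascertainment, borderline seriousness, relatedness and events before Visit 1. Its size cannot be derived from the documents. Under the Step 3 assumptions the look-back can inflate the vaccine-to-placebo ratio to at most 1.20. If the parent blind holds at Visit 1, that inflation does not follow. With up to 30 subjects per group, either effect is small beside the sampling error. The change is worth making because it is cheap and protects the by-group safety tables. The primary analysis is not in question.

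The wording mismatch stands whatever the blind's status. The protocol and SAP use different terms for the product, and the SAP window covers six months in which the protocol collects related SAEs only and no pIMDs.

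**What to change.** 1. In the synopsis, replace open. In protocol sections 3 and 5.3, add that site staff and subjects not yet unblinded stay blinded to the NTHi-Mcat-001 group until database lock after the last Visit 6. Keep an emergency code-break, allow disclosure at a subject's request with the date recorded, and limit the allocation to the sponsor staff who run the interim analyses.
2. Have pIMD classification and causality entered before any disclosure. Where a site is already unblinded, record the date.
3. Use one term in protocol 8.2.1 and SAP 6.3.1, for example *study vaccine(s), including placebo*. Start the by-group SAE and pIMD tables at Visit 1, report earlier events separately, and state that Month 14 to 20 is covered only by related SAEs.

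The cost is protocol and SAP wording, a restricted allocation list across three interim analyses, and a log of disclosure dates. Visits, samples and assays do not change. The real downside is that subjects and investigators learn individual assignments up to about 30 months later unless the subject asks.
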